6.3.4. Analyses of exploratory endpoints

Descriptive analyses of the "Full analysis set population" in subgroups:

- Proportion (95% CI) seroconverting to a positive response to SARS-CoV-2 IgG serology after two doses of vaccine, at 9 months, 12 months, 18 months, 24 months, 30 months, and 36 months after the second vaccine dose, measured in the "Two doses of vaccine population" compared with the control group.
- Humoral and cellular immune response at baseline and after vaccinations in blood and saliva
- Prevalence of escape mutations in SARS-CoV-2 sequencing in breakthrough infections.
- Prevalence of development/progression of graft-versus-host disease in allogeneic stem cell transplant recipients.
- Occurrence of biopsy-verified rejection in solid organ transplant recipients.
- Occurrence of viremia (defined as HIV RNA >50 copies/ml) after vaccination in individuals with HIV infection.
- Change in HIV DNA from study start to 3 and 6 months, 9 months, 12 months, 18 months, 24 months, 30 months, and 36 months after the second vaccine dose in people with HIV infection.
- Oral/intestinal microbiome and vaccine response in HIV-infected individuals and controls.

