5.1.2. Test subject population

Recruitment of the primary population will take place at Karolinska University Hospital. For the patient group with primary immunodeficiency, an application for data extraction from the PIDcare quality registry (National Quality Registry for Primary Immunodeficiency Diseases) will be made to identify patients who can be included in the study. The data extraction will cover diagnosis and lab values (latest IgG, IgA, IgM, and lymphocyte profile).

The control group will be recruited, for example, from among staff at Karolinska University Hospital and, if necessary, from other healthcare units or facilities, such as primary care, via the Alltid öppet app, recruitment flyers, or advertising. Healthcare personnel are recruited as a control group because of easier access to sampling and because this is a priority group for vaccination among healthy individuals. Depending on when the study can start versus the vaccine rollout for healthcare personnel, others such as relatives of healthcare personnel or study participants may also be eligible for recruitment. The age category ≥ 60 years may be difficult to recruit among healthcare personnel, which is why external recruitment outside the hospital is necessary.

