5.1.4. Exclusion criteria

1. Previous or ongoing COVID-19.
2. Has coagulation disorders, other conditions associated with prolonged bleeding time, or anticoagulant treatments, which, according to the investigator, contraindicate intramuscular injection. Conditions that can be corrected with measures such as treatment with platelet concentrates, coagulation factors, or other measures for people on anticoagulants are not exclusion criteria.
3. Planned to receive another vaccine within 14 days prior to the first dose of the study vaccine, or during the period from the first dose of the study vaccine until 14 days after the second dose of the study vaccine, and vaccination with another vaccine that, in the investigator's opinion, cannot be planned outside these time periods.
4. Pregnancy or breastfeeding.
5. Hypersensitivity to the active substance or to any of the excipients contained in the vaccine.
6. Individuals who are unable to understand the research subject information. Individuals who, for other reasons, are deemed by the investigator to be unsuitable for inclusion.

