- HIV-infected individuals and control subjects are offered participation in a study component investigating the significance of the microbiome for vaccine efficacy. Individuals who agree to participate in this component will be sent fecal sample collection kits to their homes after the video visit, or the kits will be given to them directly during the physical visit. The person can then send the fecal sample by mail to the study unit during the screening period, or drop it off on site on day 0, before or after the injection of the first vaccine dose. Saliva samples submitted in the study can be used for both antibody response and oral microbiome analyses.

5.2.2. Day 0

If study participants meet all inclusion criteria and no exclusion criteria, they can proceed to day 0, either on the same day or on another day within 28 days after screening. Day 0 visits take place at the study unit.

On day 0, the first vaccine dose is given according to the product summary, and the vaccination is registered in an internet-based reporting system for vaccinations according to healthcare routine (Vaccinera). The study unit where vaccinations are planned to be given will have the necessary equipment and medicines (adrenaline, cortisone, and antihistamine) on hand for a potential anaphylactic reaction. A doctor will be available.

Individuals with an increased risk of bleeding, such as known coagulopathy or anticoagulant treatments, will be managed according to section 5.3.1.

Day 0 samples will be taken before injection of the first dose of vaccine. Sampling according to the schedule in Table

2. For blood sample volume at each visit and total in the study for each subgroup of study participants, please see Appendix 2). Saliva will be collected by having study participants spit saliva into a clean jar for 5 minutes. It is also possible to provide a saliva sample after the vaccine dose.

Two groups of sampling are planned:

A. Group with sampling without cellular immunity.

B. Group with cellular immunity sampling (at least 40 study participants per patient group)

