6.2. Analysis populations

Population	Description of population
Full analysis set population	All study participants who have received at least one dose of vaccine
Population with two doses of vaccine	All study participants who received two doses of vaccine and had a test result at 2 weeks after the second vaccine dose.
Population with evaluable reactogenicity after dose 1	All study participants who have received at least one dose of vaccine and have at least one measurement of reactogenicity after the first dose.
Population with Evaluable reactogenicity after dose 2	All study participants who have received two doses of vaccine, and had at least one measurement of reactogenicity after the second dose.

The number and percentage of study participants who are enrolled in the study, complete the study, and discontinue the study will be presented. Reasons for discontinuation will also be presented.

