6.3. Planned analyses

6.3.1. Descriptive analyses

- The number and percentage (95% CI) of study participants with co-morbidity and other baseline characteristics.
- Previous and ongoing treatments will be summarized.
- Description of abnormal findings on complete or targeted physical examinations, vital parameters, clinical laboratory tests, and pregnancy tests.

6.3.2. Analyses of primary endpoint:

- Proportion (95% CI) receiving a positive SARS-CoV-2 IgG serology test result after two vaccine doses, three weeks after the second vaccine dose in the "population with two doses of vaccine," and having a negative SARS-CoV-2 serology test result at baseline, i.e., seroconverting.
- Chi² test is used for comparisons with the control group.

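### Exploratory humoral and cellular responses are analysed without regard to baseline infection status, so unrecognised infection can distort the comparison with controls

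*Combined protocol and SAP*

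**What the plan says.** The exploratory analyses in section 6.3.4 stand under the line "Descriptive analyses of the 'Full analysis set population' in subgroups". One item is "Humoral and cellular immune response at baseline and after vaccinations in blood and saliva". It names no population of its own, so the heading governs. The first item in the same list does name another set (the two-dose population), so the authors replaced the heading where they wanted to.

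Section 6.2 defines the full analysis set as "All study participants who have received at least one dose of vaccine". It sets no condition on serology, PCR or infection.

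The seroconversion analyses differ. Section 6.3.2 requires "having a negative SARS-CoV-2 serology test result at baseline, i.e., seroconverting", and section 4.1 defines seroconversion as occurring in seronegative people, so the 3- to 36-month seroconversion analyses carry the same limit by definition.

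At entry, section 5.1.4 excludes "Previous or ongoing COVID-19"; a positive antibody test is not listed. Section 5.2.2 says "If study participants meet all inclusion criteria and no exclusion criteria, they can proceed to day 0" and, on sampling, "Day 0 samples will be taken before injection of the first dose of vaccine". The day 0 samples include SARS-CoV-2 serology and PCR.

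**The concern.** The vaccine-response data most sensitive to earlier infection are antibody levels, neutralisation and spike-specific T and B cells. They are quantitative, and an infected person's values can be a multiple of a naive person's. These are the data for which the plan drops the baseline condition it applies to seroconversion.

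The analysis also supports a directional claim. Section 5.4.4 states the hypothesis that immunodeficient people will have lower protective antibodies and virus-specific T cells than controls. If the groups differ in their share of unrecognised infection, or in how strongly infection raises their levels, part of the observed difference reflects infection history and not response to the vaccine. The protocol accepts that the routine test cannot tell the two sources apart (sections 3.2 and 5.5.9) and that infection may raise antibodies (section 2.2). Its argument in section 3.2 for crediting the vaccine relies on baseline serology and PCR, and section 6.3.4 makes no use of either.

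**Working it through.** The plan states no figure on this point, so there is none to reproduce. The check has two parts.

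**1. Can infected people reach the analysis set?**

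- Screening is by video where possible (section 5.2.1), so it may involve no sampling.
- Table 2 marks the eligibility criteria at screening and again on day 0. Serology and PCR are sampled on day 0, immediately before dose 1. No step makes the dose, or membership of any analysis set other than that for seroconversion, depend on the result.
- Sections 6.2 to 6.4 contain no rule that excludes, censors or stratifies by baseline serology, baseline PCR or later infection for the humoral and cellular item.

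Recognised COVID-19 is kept out; unrecognised past or current infection is not. The set is in practice everyone dosed who has a sample. For cellular results that means sampling group B, at least 40 per patient group (section 5.2.2).

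**2. How far could the comparison move?**

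Inputs, all assumed because the documents give neither:

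- s = share of a group previously infected: 5% in one group, 15% in the other.
- k = factor by which infected people's levels exceed those of naive people: 3 to 10, the same in both groups.

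Infection multiplies a group's geometric mean by k^s. The ratio of the two groups' geometric means is therefore multiplied by k^(s1 − s2), here k^(0.15 − 0.05) = k^0.10:

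- k = 3: 3^0.10 = 1.12
- k = 10: 10^0.10 = 1.26

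With equal shares and equal k the exponent is zero and the ratio does not move. In a cellular group of 40, shares of 5% and 15% are 2 and 6 people. Section 6.4 specifies median and IQR for non-normal values, and a median would usually move less than these factors.

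**Direction.** If the larger share is among controls, the gap widens; if among patients, it narrows. Equal shares do not guarantee balance either. For a yes/no response with naive response rate p and infected share f, and assuming every infected person is positive, the observed rate is p + f(1 − p). Borrowing the seroconversion rates in section 2.1 as illustrative values of p, with f = 10% assumed:

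- p = 43% (organ transplant): 43 + 0.10 × 57 = 48.7%, up 5.7 points
- p = 72% (all patients): 72 + 0.10 × 28 = 74.8%, up 2.8 points

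Infection adds more where the vaccine response is weaker, which would narrow the gap to controls.

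**The case against.** The strongest reply is that these are descriptive, exploratory analyses. Responses are shown at baseline as well as after vaccination, so pre-existing immunity is visible. Known COVID-19 is excluded. The authors are aware of the issue: section 2.2 names infection as a source of antibody rise, and the version 7.0 addition to section 2.1 reports a response after a third dose together with infection.

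Much of this stands, and it rules out three stronger readings that a reader might infer:

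- That infection-induced immunity is passed off as vaccine response. The documents show infection being named when results are described. What is missing is a rule in the analysis plan.
- That the gap is inflated because controls are hospital staff with more past infection. Section 5.1.2 says "The control group will be recruited, for example, from among staff at Karolinska University Hospital", but only as an example. It also lists primary care, advertising and relatives, and calls outside recruitment necessary for those aged 60 or over, who are 30 of the 90 controls. No infection rate is given for any group.
- That people infected after baseline should simply be removed. Poor vaccine response may itself lead to infection, so removal would select the better-protected patients, and by 36 months the loss could be large.

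What does not stand is that the exploratory label settles the matter. Section 5.4.4 attaches a directional hypothesis to these data, and showing baseline values does not say which participants the group comparison rests on.

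**Conclusion.** The point holds as a choice of population. The set named in section 6.3.4 admits people with unrecognised infection at baseline to the humoral and cellular comparisons with controls, while the seroconversion endpoints exclude anyone seropositive at baseline. Under the assumed shares and 3- to 10-fold levels, the shift in the geometric-mean ratio is about 1.12 to 1.26. It is zero if shares and fold-increases are equal, and usually smaller on medians. Both inputs are assumptions, and the direction is open. The primary endpoint and the later seroconversion endpoints are not affected by this baseline point. It is worth correcting because the status data are already planned and the remedy is a wording change.

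**What to change.** In section 6.3.4, define the main set for humoral and cellular responses as participants with negative day 0 serology and negative day 0 PCR, and negative nucleocapsid IgG where measured. The detailed assay in section 5.4.2 already includes a nucleocapsid antigen, and the vaccine encodes only spike (section 2.1), so that marker points to infection. Show baseline-positive people in a separate row and keep the full analysis set as a sensitivity table.

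For infection after baseline, keep people in the main table and present results at each visit by documented infection status and by extra vaccine doses received. Both are already to be recorded (sections 5.2.9 to 5.2.14 and 5.4.8).

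Eligibility, dosing, visits and samples do not change. The cost is slightly fewer people in the main table. One limitation should be stated: antibody-based markers may miss past infection in patients who form few antibodies, so the restriction may clear infected controls more completely than infected patients. PCR during follow-up is prompted by symptoms, so documented status will also miss silent infections.

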6.4. Statistical methods

Continuous variables will be presented with mean and standard deviation [SD] for normally distributed values, and median and interquartile range (IQR) for non-normally distributed values. Categorical variables will be presented as frequency distributions.

Comparisons between patient groups and the control group will be made using the Chi-square test. P-values will be adjusted for multiple comparisons where necessary.

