2.2. Expected results

We expect that some immunosuppressed patients will have a lower degree of immune activation and thereby potentially poorer immunity, compared with

immunocompetent individuals. Individuals who have an absence or partial deficiency in their ability to form antibodies can be expected to develop T cell immunity in certain cases. The degree of immunological response is expected to decrease over time, but it is difficult to predict the duration of a strong immunological response, as we currently lack long-term data. Reactogenicity may be milder in immunosuppressed individuals compared to immunocompetent individuals.

We expect the antibody response to decrease over time, but booster doses and/or new SARS-CoV-2 infections may increase the antibody response, while in some individuals a low/negative antibody response may continue. With the development of new variants, neutralisation capacity may change.

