5. STUDY DESIGN

5.1. Assessments and study procedures

5.1.1. Study participants

Immunosuppressed individuals (primary study population) and immunocompetent individuals (control population) are planned to receive two doses of the Comirnaty vaccine in an open-label cohort study without randomization or blinding. Study participants would have been offered vaccination within the Stockholm Region, regardless of whether they participated in the study or not.

A total of 540 individuals who wish to be vaccinated against COVID-19 are planned to be included in the study.

Within the primary study population of immunosuppressed individuals, 450 individuals are planned to be included. The goal is to include 90 individuals per patient category:

- Patients with primary
- immunodeficiency Patients with HIV
- infection
 - Patients who have undergone allogeneic stem cell transplantation/CAR T cell therapy
- Patients who have undergone solid organ transplantation Patients with
- chronic lymphocytic leukemia

We plan to include patient groups with both primary immunodeficiency and secondary immunodeficiency (HIV infection, allogeneic stem cell transplantation/CAR (chimeric antigen receptor) T cell therapy, solid organ transplantation, and chronic lymphocytic leukemia) among a large and heterogeneous group of all immunosuppressed patients in specialized care at the hospital. This is because these patient groups may be interesting to study from an immunological point of view, as different parts of the immune system are suppressed, and we have well-characterized patient groups at participating study units that are suitable for study. The patients attend regular check-ups at the outpatient clinic at Karolinska University Hospital and may form the basis for inclusion.

The control group (90 people in total) is planned to be recruited in the following age groups: 18-39 years (n=30), 40-59 years (n=30), and >60 years (n=30).

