5.8.3. Assessment of local and systemic reactogenicity

1.1.1.3 Assessment of local reaction at the injection site

The occurrence of pain, redness, and swelling at the injection site is reported in a diary completed by the patient for the period from the vaccine dose to 7 days after the dose for both the first and second vaccine doses. Local bleeding is observed by staff after injection during the observation period. For individuals who have difficulty filling in a diary, study staff will contact the patient on days 2 and 7 after the vaccine dose to collect data by telephone.

The rationale for the 7-day period after the vaccine dose is that local reactions have been studied in 8,183 study participants within 7 days after injection, and these reactions usually began within two days after vaccination and disappeared after 1-2 days. Only 1% reported severe pain, and a lower frequency was reported for redness or swelling. These reactions were less common in people over 55 than in younger people. We do not expect a higher frequency or more severe degree of these local reactions, possibly the opposite in immunosuppressed individuals. An exception may be local bleeding at the injection site, due to existing medical conditions with coagulopathy or anticoagulant treatments.

Table 1. Local Reaction Grading Scale

	Mild (Grade 1)	Moderate (Grade 2)	Severe (Grade 3)	Potentially Life Threatening (Grade 4)
Pain at the injection site	Does not interfere with activity	Interferes with activity	Prevents daily activity	Emergency room visit or hospitalization for severe pain
Redness	>2.0 cm to 5.0 cm (5 to 10 measuring device units)	>5.0 cm to 10.0 cm (11 to 20 measuring device units)	>10 cm (≥ 21 measuring device units)	Necrosis or exfoliative dermatitis
Swelling	>2.0 cm to 5.0 cm (5 to 10 measuring device units)	>5.0 cm to 10.0 cm (11 to 20 measuring device units)	>10 cm (≥ 21 measuring device units)	Necrosis

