6.3.3. Analyses of secondary endpoints

- Proportion (95% CI) seroconverting to a positive response to SARS-CoV-2 IgG serology after two doses of vaccine, at 3 months and 6 months after the second vaccine dose, measured in the "two-dose vaccine population" compared with the control group.
- Proportion (95% CI) experiencing adverse events, with AE/SAE/SUSAR. Number and proportion (95% CI) experiencing local reactions and systemic reactions are measured in the "Full analysis set population".
- Proportion (95% CI) receiving a new diagnosis of SARS-CoV-2 infection through a positive PCR test is measured in the "Full analysis set population."

- Comparisons are made with the control group.

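### Local reactions are compared with controls by an unadjusted chi-square test, although the protocol says they vary with age and only the controls have age quotas

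*Combined protocol and SAP*

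**What the plan says.** Local reactions are a secondary endpoint (section 4.2). Section 6.3.3 has the number and proportion "experiencing local reactions and systemic reactions are measured in the" full analysis set, and closes its list with "Comparisons are made with the control group".

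Section 6.4 names one method for this: "Comparisons between patient groups and the control group will be made using the Chi-square test". It then adds "P-values will be adjusted for multiple comparisons where necessary". Nothing in sections 6.1 to 6.4 provides for stratification, standardisation, matching or regression.

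Section 5.1.1 describes a cohort without randomisation. The 90 controls are filled by quota, 30 in each of three age bands. Each patient category has a target of 90 and no age quota; the only age criterion is the lower limit of 18 years (section 5.1.3).

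On age, section 5.8.3 says of local reactions: "These reactions were less common in people over 55 than in younger people". On the expected direction in patients it continues: "We do not expect a higher frequency or more severe degree of these local reactions, possibly the opposite in immunosuppressed individuals". Section 2.2 takes the same view: "Reactogenicity may be milder in immunosuppressed individuals compared to immunocompetent individuals".

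**The concern.** The protocol names age as a determinant of this outcome, fixes the age mix on one side of the comparison only, and then plans a test that ignores age. Nothing in the design makes the age mix of a patient group agree with the controls' even thirds. In an older group, age alone would lower the rate of local reactions, which is the direction the protocol already expects for immunosuppressed people. In a younger group, age would raise the rate and could hide a real reduction.

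The multiplicity adjustment does not deal with this. It moves the significance threshold and leaves the bias in the estimated difference where it was.

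At stake is the reading of one secondary tolerability comparison: a difference due to age could be reported as an effect of immunosuppression, or a real one missed. The proportion with 95% CI within each group remains a valid description.

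**Working it through.** The plan gives no power or expected rate for local reactions (the power statement in section 6.1 concerns seroconversion), so there is no figure of its own to reproduce. What follows is illustrative.

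**Inputs from the documents.** 90 patients per group; 90 controls, of whom 30 are in the oldest band; alpha 0.05 (section 6.1).

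**Assumed.** Local reactions in 80% under 60; a drop of *d* points from 60 (5, 10, 20 or 30); a share *s* of the patient group aged 60 or over (20 to 90%); no true effect of immunosuppression.

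**Bias.** The expected rate is 80 − *d*/3 in controls and 80 − *d*·*s* in patients, so the bias is −*d*(*s* − 1/3). For *d* = 20 and *s* = 0.70 it is −20 × (0.70 − 0.333) = −7.33 points.

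**False positives.** Each arm's count is a sum of two binomials: controls 60 and 30; patients 72/18, 54/36, 45/45, 27/63 or 9/81. Summing the joint probabilities where the two-sided Pearson statistic exceeds its critical value gives the exact rejection rate. Each cell shows bias in points, then per cent rejected at 0.05.

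| Age effect | s = 20% | 40% | 50% | 70% | 90% |
|---|---|---|---|---|---|
| 5 points | +0.67; 4.99 | −0.33; 4.89 | −0.83; 5.06 | −1.83; 5.84 | −2.83; 7.20 |
| 10 points | +1.33; 5.29 | −0.67; 4.90 | −1.67; 5.55 | −3.67; 8.53 | −5.67; 13.73 |
| 20 points | +2.67; 6.42 | −1.33; 4.93 | −3.33; 7.27 | −7.33; 18.13 | −11.33; 36.67 |
| 30 points | +4.00; 8.07 | −2.00; 4.77 | −5.00; 9.67 | −11.00; 33.63 | −17.00; 66.71 |

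**After a multiplicity correction.** At 0.01 (Bonferroni for five groups, assumed), the rates for 50, 70 and 90% aged 60 or over are 1.0, 1.3 and 1.8% with a 5-point effect, 1.8, 6.3 and 17% with 20 points, and 2.6, 14 and 41% with 30 points. The bias is unchanged.

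**A younger group.** With 20% aged 60 or over, a 20-point age effect and a true 15-point reduction, power at 0.05 is 42% for the crude test and 58% for the age-stratified Cochran-Mantel-Haenszel test.

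**Stratified analysis.** In 200,000 simulations per scenario the Cochran-Mantel-Haenszel test rejected in 4.9 to 5.1%. The 95% CI for the Mantel-Haenszel risk difference covered in 93.6 to 94.7%. With a 20-point effect and 50, 70 and 90% aged 60 or over, a crude Wald interval covered in 92.4, 81.2 and 62.7%.

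**Precision.** For *d* = 20, *s* = 50%:
- Crude variance: (60×0.16 + 30×0.24 + 45×0.16 + 45×0.24)/90² = 34.8/8100 = 0.00430, so the standard error is 6.55 points.
- Mantel-Haenszel weights: 60×45/105 = 25.71 and 30×45/75 = 18.00, total 43.71.
- Stratified variance: [25.71²×0.16×(1/60 + 1/45) + 18.00²×0.24×(1/30 + 1/45)]/43.71² = 8.43/1911 = 0.00441, so the standard error is 6.64 points, a rise of about 1%.
- By the same formula the rise is under 1% with 40% aged 60 or over, 8% with 70% and 24 to 26% with 90%.

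**Different assumptions.** Splitting at 55, with 80–85% reacting up to 55 and 65–75% above it, and 33% or 40% of controls over 55, a normal approximation at 90 v 90 gives about 5% false positives with 40% of patients over 55, 9 to 20% with 80%, and 12 to 26% with 90%.

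**Cut point.** Suppose a 20-point effect starts at 55, patients number 13/14/63 in the control bands, and 25% of controls and 50% of patients in the 40–59 band are above the cut. The crude bias is −20 × [(7 + 63)/90 − (7.5 + 30)/90] = −7.2 points. Stratifying on the control bands, with weights 9.07, 9.55 and 20.32, leaves −20 × 0.25 × 9.55/38.94 = −1.2 points. With 10% v 50% above the cut it leaves −2.0.

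**The case against.** The plan does not claim a causal comparison for this endpoint. The objective is tolerability in the people studied, and section 6.1 describes the study as exploratory. If one group is older and reacts less, the crude proportions do differ, and a test that detects this is not wrong; the error lies in attributing the difference to immunosuppression. That is fair and limits the weight of the point. Still, a formal comparison with controls is planned, and sections 2.2 and 5.8.3 invite that attribution.

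The harm also depends on facts the documents do not give. With 40% of patients aged 60 or over nothing happens, and with 50% the rates stay between 5.1 and 9.7%. The largest figures need a strongly older group and a large age effect together. This stands. Nor could a 20- or 30-point drop apply to redness alone, which Table 1 in section 3.1 puts below 1 in 10; those rows concern any local reaction.

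Age stratification does not isolate immunosuppression. Controls may be hospital staff, must have no significant co-morbidity, and report in open-label diaries. This stands too. The stratified test holds its level partly by construction, since age is the only difference simulated. The main simulations used two strata cut at 60; a three-stratum run cut at 55 also held 4.9% with no bias. Power for the stratified test in older groups was not computed; only the loss of precision is shown.

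**Conclusion.** The concern holds, as a minor one. The plan compares local reactions with controls by a crude test while stating that age affects them and controlling the age mix of the controls only. Whether the comparison is biased, which way and by how much cannot be told from the documents. Under the assumed rates the effect is negligible when age mixes are close, modest at 50% aged 60 or over (bias −0.8 to −5.0 points), and large only with a marked imbalance and a large age effect together. It touches one secondary comparison. The documents state no age effect for systemic reactions or seroconversion, so the point does not extend to them on this evidence.

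**What to change.** In sections 6.3.3 and 6.4, add for each patient group against controls an age-stratified or age-standardised risk difference with 95% CI for local reactions after each dose. One form is Mantel-Haenszel over 18–39, 40–55 and over 55; another uses age as collected. Cut at 55, because section 5.8.3 refers to 55 whereas the control bands cut at 60. Keep the crude chi-square test beside it, in the same analysis set and with the same multiplicity adjustment, and show age by group in the baseline summary already planned in section 6.3.1. The same analysis of systemic reactions and seroconversion would be an optional sensitivity check.

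No new data are needed: age is in both eCRF base modules (Appendix 1) and the diaries end 7 days after each dose. Section 2.1 already reports results from two weeks after the second dose, so the analysis must be labelled supplementary and added after results were known. The other cost is precision, which is small unless a group is much older than the controls.
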